## Project Description

The objective of this randomized clinical trial is to test whether administration of live attenuated MMR vaccine (measles mumps rubella; Merck) to eligible adults at risk for contracting COVID-19, can induce non-specific trained innate immune leukocytes that can prevent/dampen pathological inflammation and sepsis associated with COVID-19 infection, if exposed. Mechanistically, we will monitor whether MMR (booster) vaccination induces non-specific immune leukocytes that limit pathological inflammation and sepsis, a critical sequelae associated with COVID-19 infection. The use of live attenuated vaccines (LAV) has been shown to provide beneficial non-specific effects, including reduced mortality and hospitalization due to unrelated infections (1-3). These non-specific effects are a result of inducing "trained innate immunity" via leukocyte precursors in the bone marrow to function more effectively against broader infectious insults (4,5). Work from our laboratory demonstrated that vaccination with a live attenuated fungal strain induces "trained innate" protection against lethal polymicrobial sepsis by myeloid-derived suppressor cells (MDSCs) (5-7). Mortality in COVID-19 cases is strongly associated with progressive lung inflammation and eventual sepsis (8). According to CDC guidelines, vaccination with MMR in immunocompetent individuals has no contraindications and may be especially effective for healthcare workers and first responders who can easily be exposed to any number of infections. While other current clinical trials have been initiated with the live attenuated BCG vaccine for the purpose of inducing cells trained for non-specific immune enhancement against COVID-19, (<https://www.sciencemag.org/news/2020/03/can-century-old-tb-vaccine-steel-immune-system-against-new-coronavirus>;  
<https://www.nytimes.com/2020/05/01/opinion/sunday/coronavirus-vaccine-innate-immunity.html>), we herein propose a randomized control clinical trial with live attenuated MMR vaccine (repurposed) to induce trained non-specific MDSCs as a preventive measure to inhibit the severe lung inflammation/sepsis associated with COVID-19 infection. Our overarching hypothesis is that administration of the live attenuated vaccine in adults will induce the trained innate MDSCs that can serve as an immune-based preventive against the severe sequelae of COVID-19 infection. Accordingly, this trial has potential for high impact as a "low risk-high reward" response to the COVID-19 pandemic as we have recently reported (9).

## Experimental Design

### Clinical Design.

Eligible healthcare workers (HCW), first responders, and non-healthcare individuals in the greater New Orleans area (n=60) meeting eligibility criteria will be enrolled into a 12 month study conducted by the Louisiana State University Health Sciences Center Clinical & Translational Research Center (LSUHSC CTRC) clinical staff affiliated with the Louisiana Clinical and Translational Research Science (LA CaTS) Center and blindly randomized to receive the live attenuated M-M-R® II vaccine or placebo (sterile

saline) via subcutaneous injection in the arm at a baseline visit following informed consent. Subjects will be recruited from the LSUHSC, LSU Dental School, local hospitals, long-term care facilities, EMS stations, and the general community throughout the greater New Orleans area by distributing recruitment flyers, social media postings, and by designated on-site recruitment activities conducted by study personnel within local facilities. The flyers and social media postings will have contact information for individuals to call for more information or to schedule an appointment. Additionally, subjects may be referred to the study by other participants or individuals aware of study activities. Subject consenting, interviewing, vaccine administration and biospecimen collection will be performed by the CTRC staff, under full Personal Protective Equipment (PPE) protection. Following informed consent, subjects will be asked to complete the Baseline Demographic & History Questionnaire disclosing their demographic information, employment, medication, vaccination, and medical history. Specifically, the medical history will place emphasis on the presence of diabetes, hypertension, heart disease, and their treatments/medications. Subjects will then have their height, weight, body mass index (BMI), vital signs, and pulse oximetry measured. Female subjects of childbearing potential will be given a urine-based pregnancy test. Approximately 30cc of blood will be collected along with a nasopharyngeal swab for baseline laboratory analyses (serology, RNA, flow cytometry). When available, a finger prick blood sample will be obtained in addition to the other biospecimens for SARS-CoV-2 antibody testing. SARS-CoV-2 antibody testing will occur at the baseline visit, optional 12 month visit, and upon a positive COVID-19 result by nasopharyngeal swab collected in the CTRC (at the subject's availability). Those subjects that satisfy the inclusion and exclusion criteria (Eligibility Criteria) will be blindly randomized to receive the live attenuated M-M-R ® II vaccine or placebo (sterile saline) via subcutaneous injection. Repeat biosampling will occur on days 14 (+/- 2 days), 30 (+/- 2 days), 60 (+/- 4 days), and at an optional 12 months (+/- 7 days) post-vaccination. At each follow-up visit, anthropometric measurements, vital signs measurement, and symptom assessment for the presence of symptoms related to COVID-19 infection (fever, headache, myalgia, cough, loss of taste or smell, breathing problems), general well-being (i.e., pain, dental concerns, sleep patterns, general stress level, fatigue), and any changes in medications, medical status, and employment will be collected utilizing the Follow-up Symptom & History Questionnaire. Telephone follow-up calls utilizing the Follow-up Symptom Assessment & History Questionnaire will be made on a monthly basis between the 60 day follow-up and the optional 12 month endpoint visit at designated timepoints. Subjects will additionally be asked to come into the clinic at their convenience for a mid-point study visit and follow-up biospecimen collection (blood only). Subjects will have the option to schedule this mid-point visit at 6, 7, or 8 months after enrolling into the study. Subjects will have the option to schedule a 12 month follow-up visit where anthropometric measurements will be taken, vital signs measured, a symptom assessment for the presence of symptoms related to COVID-19 infection taken, and a fingerprick for blood sampling to assess the presence of SARS-CoV-2 antibodies will be administered when available. Should a subject develop symptoms potentially associated with COVID-19 infection at any point during the 12-month study period, he/she will be seen in the clinic by the Infectious Disease (ID) Co-investigator

and a repeat collection of blood and nasopharyngeal biospecimens will be performed for analysis, and the subject will be asked to complete the Follow-up Symptom & History Questionnaire. Subjects will be asked to report the development of any potential COVID-19 infection related symptoms or positive COVID-19 infection testing outside of the study, as well as any symptoms potentially related to MMR vaccination. Should a subject become admitted to the hospital related to COVID-19 infection, in-patient information will be obtained via the electronic medical record (EMR) when available.

Subjects will also be enrolled and followed at additional local facilities within the greater New Orleans area. If enrolled at a local facility other than the LSUHSC CTRC, subjects will have their baseline visit conducted on-site at the enrolling facility. Should work schedules prohibit follow-up visits from being performed at the LSUHSC CTRC, subjects will have the option to have them conducted at the enrolling collaborating site. When possible, follow-up visits will be completed at the LSUHSC CTRC. The same biospecimens and study procedures will be collected and followed at all collaborating sites for all study visits.

Subjects will be compensated \$25.00 for each clinic study visit

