### Risks

While there may be psychological, social, legal, and economic risks associated with COVID-19 infection, it is not expected that participation in the proposed project is associated with any of these risks, both within the MMR and placebo groups. The major risks associated with study participation are related to the MMR vaccine. There are few contraindications. The most frequently observed side effects are associated with the MMR vaccine are mild and include dizziness, visual changes, hypotension, and fainting, soreness or rash at the injection site, a generalized body rash, fever, and swelling in the glands of the cheek or neck. More serious reactions associated with the vaccine are rarely seen and include a life threatening allergic reaction, seizures which are often associated with fever, temporary pain and stiffness in the joints, pneumonia, swelling of the brain and/or spinal cord covering, and temporary low platelet count which can cause unusual bleeding or bruising. Additionally, people with serious immune system problems can develop a life threatening infection. The risks associated with phlebotomy include pain or bruising at the needle site, dizziness, and syncope. The risks associated with nasopharyngeal swabbing can include gagging and pressure or discomfort upon swab insertion and a small amount of bleeding after the procedure.

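### The plan specifies no summary of vaccine reactions by arm, and mild MMR reactions rest mainly on what blinded participants choose to attribute to the vaccine

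*Combined protocol and SAP*

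**What the plan says.** All places are in the combined protocol and SAP.

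- **Risks** attributes the major risks of taking part to the vaccine. Its frequent, mild reactions include "soreness or rash at the injection site, a generalized body rash, fever, and swelling in the glands of the cheek or neck", along with dizziness, visual changes, hypotension and fainting. A second group of serious reactions is described as rare.
- **Clinical Design**, on follow-up visits, specifies a "symptom assessment for the presence of symptoms related to COVID-19 infection (fever, headache, myalgia, cough, loss of taste or smell, breathing problems"). It adds items on pain, sleep, stress, fatigue and dental complaints. An open item needs no attribution to the vaccine: "any changes in medications, medical status, and employment will be collected utilizing the Follow-up Symptom & History Questionnaire". The same sentence begins "At each follow-up visit, anthropometric measurements, vital signs measurement".
- **Clinical Design**, on vaccine reactions, asks participants to report COVID-19 symptoms or outside positive tests, "as well as any symptoms potentially related to MMR vaccination". No checklist, grading or reporting window is described.
- **Clinical Design**, on timing: "Repeat biosampling will occur on days 14 (+/- 2 days), 30 (+/- 2 days), 60 (+/- 4 days"). Day 14 is therefore the first scheduled contact after the injection.
- **The outcome-measures paragraph after Eligibility Criteria** has MDSC levels as primary and COVID-19-related measures as secondary. It has no safety outcome.
- **Data analysis** summarises demographics, MDSCs and COVID-19-related clinical characteristics by group, and limits secondary-outcome analyses to participants who test positive for COVID-19. It does not mention vaccine reactions.

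**The concern.** The trial has a blinded saline arm, which is the best available means of separating what the vaccine causes from background complaints. That works well only if the same events are sought in the same way in both arms and then set side by side. Here the named questions are aimed at COVID-19, and the one vaccine-specific route asks the participant to judge causality before reporting. A sore arm, a transient rash or a dizzy spell in the first days may be forgotten by day 14, or dismissed as unrelated. Even what is reported has no planned place in the analysis.

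At stake is the tolerability information from a trial that enrols adults aged 18 to 85, calls its approach low risk, and would grow to 400-500 participants if further funding were found. The primary MDSC result is not affected.

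**Working it through.** The documents give no figure for reaction capture or reaction rates, so there is no figure of theirs to reproduce. The check is a count, a reading of the analysis plan, and arithmetic on what 60 participants can show.

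**1. Reactions listed in Risks against follow-up content in Clinical Design**

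Frequent (8): dizziness, visual changes, hypotension, fainting, injection-site soreness or rash, generalised rash, fever, gland swelling. Serious (6): severe allergic reaction, seizures, joint pain and stiffness, pneumonia, swelling of the brain or spinal cord covering, low platelets. Total 8 + 6 = 14; the total is approximate because it depends on how entries are split.

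- Asked by name: fever (1).
- Touched indirectly: hypotension through vital signs, joint pain through the pain item, pneumonia through cough or breathing problems (3).
- Not named: 14 - 1 - 3 = 10.

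Of those 10, four are serious events (allergic reaction, seizures, brain or cord swelling, low platelets) that could come to light as a change in medical status. The other six are frequent reactions: injection-site soreness or rash, generalised rash, gland swelling, dizziness, fainting and visual changes. A participant may not regard these as a change in medical status, so they depend mainly on self-attributed reporting. Vital signs at day 14 would not show hypotension that had resolved earlier.

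**2. What the analysis plan would tabulate**

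Fever could enter the by-arm summary as a COVID-19-related characteristic. The fatigue and stress comparison is a secondary outcome, so it is confined to COVID-19-positive participants: at the assumed 10% prevalence, 0.10 x 50 = 5 people. Changes in medical status and reported vaccine reactions appear in no planned summary.

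**3. What a by-arm table could show**

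Input: 60 enrolled, taken as 30 per arm. The sample-size section uses 25 per group out of 50, but 1:1 allocation of the 60 is my assumption.

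- One-sided 95% upper limit with zero events: 1 - 0.05^(1/n). For n = 30 this is 1 - 0.05^(1/30) = 9.5%; for n = 25 it is 11.3%.
- Chance of seeing at least one case of a reaction with a true rate of 1% (assumed) among 30: 1 - 0.99^30 = 26%. For a true rate of 10% (assumed): 1 - 0.90^30 = 96%.
- Fisher's exact test, two-sided 0.05, 30 per arm: the smallest significant split against zero is 6/30 versus 0/30. Power at assumed true rates:
  - 50% versus 10%: 91%
  - 40% versus 10%: 71%
  - 30% versus 5%: 63%
  - 20% versus 5%: 24%

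Common reactions with a large difference between arms are within reach; rare ones are not. The table should therefore be descriptive, with intervals.

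**The case against.** The strongest reply has five parts.

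1. *Follow-up is not limited to COVID-19 symptoms.* Vital signs, pain, and changes in medications or medical status are collected in both arms without attribution. This stands. A reader might infer that everything except fever is left to self-attributed reports; the text does not support that, least of all for serious events. The gap concerns the mild, frequent reactions.

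2. *Both blinded arms receive the same request, so reports could be tabulated by arm.* This stands. A reader might infer that the placebo group cannot show what the vaccine caused, or that no usable reaction rate can result. Both go too far. The comparison is unplanned and would be weakened by self-attribution and recall, but it is not impossible. Perceived allocation can also colour answers to yes/no items, so the fix reduces this problem without removing it.

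3. *Fever can be read against SARS-CoV-2 RNA results*, since swabs are planned at days 14, 30 and 60 and when symptoms arise. This stands: the text does not support the inference that a vaccine fever must be misclassified as COVID-19. Nor does it show a conflict over who reviews reactions. Participants with COVID-19-like symptoms see the infectious disease co-investigator whatever the cause, and Risks is silent on review.

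4. *The questionnaire is not in the documents.* The count describes the protocol's summary of it, and the form may ask more. If so, the protocol should say so; the missing analysis remains.

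5. *Estimating reaction rates for an existing, repurposed vaccine is not an objective, and 60 people cannot characterise rare events.* Both are true. This limits the priority and calls for a descriptive table, but a blinded control arm is already in the design and using it costs little.

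**Conclusion.** The point holds in a limited form. Of about 14 reactions named in Risks, 1 is asked about by name, 3 are touched indirectly and 10 are not named. Six of those 10 are frequent, mild reactions that rely mainly on a blinded participant's own attribution, with first scheduled contact at day 14. No outcome or analysis summarises reactions by arm.

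This is a worthwhile and cheap improvement, not a defect that undermines the trial. It rests on the protocol's description of the questionnaire being reasonably complete, and the 9.5% limit also assumes 30 injected per arm. I have not scaled that limit by a reporting fraction. A reader might be tempted to, but the documents give no basis for one.

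**What to change.** **Questionnaire.** Add the reactions that participants can observe to the existing Follow-up Symptom & History Questionnaire as yes/no items with onset date and severity: injection-site soreness or rash, generalised rash, gland swelling, dizziness, fainting, visual changes, joint pain or stiffness, and allergic reaction. Keep fever, with an onset date. Ask in both arms at days 14 and 30 about the period since injection, regardless of presumed cause. If the form already has these items, list them in Clinical Design.

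**Diagnosed events.** Record low platelets, seizure, pneumonia and brain or spinal cord swelling through the existing medical-status item, since participants cannot reliably answer for most of these on a symptom checklist.

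**Data analysis.** Add a descriptive table of each reaction by arm for everyone injected, with the risk difference and its 95% CI, showing fever alongside the swab result.

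**Limits.** State that, with about 30 per arm, zero events still leaves a one-sided 95% upper limit of 9.5%, so rare reactions cannot be excluded.

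**Cost.** About ten extra checklist items, a few minutes per visit and one table. No added visits, samples or participants.

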### **Eligibility Criteria**

#### Inclusion Criteria:

- 18-85 years of age
- Able to provide a signed and dated informed consent
- Able to provide pre-randomized blood specimen

#### Exclusion Criteria:

[figure not shown]
- Any known MMR vaccine contraindication
- Fever
- Weakened resistance toward infections due to a disease in/of the immune system
- Individuals receiving medical treatment that affects the immune response or other immunosuppressive therapy in the last year (see excluded medications)
- Individuals with a congenital cellular immunodeficiency
- Individuals with a malignancy involving bone marrow or lymphoid systems
- Individuals with any serious underlying illness (such as malignancy). ***People with cardiovascular disease, hypertension, diabetes, and/or chronic respiratory disease are eligible if not immunocompromised (at the discretion of the ID Co-investigator)***
- Individuals with known or suspected HIV infection, even if asymptomatic or has normal immune function (Due to the risk of disseminated MMR infection)
- Individuals with an active skin disease such as eczema, dermatitis or psoriasis at or near the site of vaccination. ***A different site can be chosen if necessary***
- Pregnant or women who think they may test positive for pregnancy in the next month following MMR vaccine administration

- Individuals who have received a MMR or another live vaccine (i.e., Zostavax, nasal spray flu vaccine) within the last year
- Individuals requiring another live vaccine to be administered within the month following study enrollment/randomization
- Individuals with known anaphylactic reaction to any of the ingredients present in the MMR vaccine

### Laboratory Design

Blood samples will be used for leukocyte analyses, and presence of SARS-CoV-2 and measles, mumps, and rubella antibodies. Nasopharyngeal sampling will be used to detect the presence SARS-CoV-2 RNA. Urine will be used for the pregnancy test. *Peripheral MDSC Analysis:* Whole blood samples will be shipped to a commercial fee-per-sample flow cytometry testing facility (Flow Contract Site Laboratory, Bothell, WA) and analyzed for M-MDSCs ( $CD33^{\text{high}}CD14^{\text{high}}\text{HLA-DR}^{\text{dim}}$ ) and G-MDSC ( $CD33^{\text{high}}CD66b^{\text{high}}\text{HLA-DR}^{\text{dim}}$ ) populations (see figure). For the MMR group samples will be evaluated at baseline, 14, 30, and 60 days post-vaccination. For the placebo group, although blood will be drawn at the same times, only the baseline, 30-day, and 12-month samples will be evaluated for MDSCs.

*M/M/R Virus Serological Analysis:* Blood serum will be analyzed for measles, mumps, and rubella virus IgG in the PI laboratory by ELISA (MyBioSource; San Diego, CA) at baseline. The measles antibody titers will be measured at all follow-up visits as a positive control for vaccine efficacy. *COVID-19 PCR Detection:* Nasal swabs will be tested for SARS-CoV-2 RNA by our co-investigator [name] using RT-qPCR Rapid Detection Kit (MyBioSource; San Diego, CA). *COVID-19 Serological Analysis:* Finger prick blood sample will be obtained and tested for the presence of antibodies against SARS-CoV-2 IgG on site in the CTRC by laminar flow test kit (Ray Biotech). If the laminar flow kits are not available in high enough quantities the serology will be conducted in the PI lab by 2019-nCoV/Coronavirus ELISA using the serum (MyBioSource; San Diego, CA). All serum samples will be stored. For those individuals that test positive for COVID-19, IgG antibodies to measles, mumps, and rubella viruses (MyBioSource) will be monitored (in the PI laboratory) and used for correlates to health status. This will include MMR and placebo subjects. Should other correlates for immune mediators be of interest to evaluate (parameters tested in other clinical trials, i.e., BCG trials) the stored specimens can be used for analyses.

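### MDSC assay times differ by arm, so a day-14 assay marks an MMR subject before the day-30 primary sample is read, and the plan does not ensure a masked assessor

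*Combined protocol and SAP*

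**What the plan says.** The Clinical Design section states that eligible subjects "will be blindly randomized to receive the live attenuated M-M-R ® II vaccine or placebo (sterile saline) via subcutaneous injection". It names no role as blinded.

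The Laboratory Design section then sets two MDSC schedules. For vaccine recipients, "For the MMR group samples will be evaluated at baseline, 14, 30, and 60 days post-vaccination". For placebo recipients, "although blood will be drawn at the same times", "only the baseline, 30-day, and 12-month samples will be evaluated for MDSCs".

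On the route of the samples, the same section says "Whole blood samples will be shipped to a commercial fee-per-sample flow cytometry testing facility". On storage it says "All serum samples will be stored"; nothing comparable is said of the whole blood used for flow cytometry. The two MDSC populations are defined by high and dim marker expression, with reference to a figure that is not available in the text reviewed.

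The power section sizes the trial on the 30-day fold change in MDSCs. The Data analysis section has CTRC staff carry out the randomization, and Clinical Design adds that "Subject consenting, interviewing, vaccine administration and biospecimen collection will be performed by the CTRC staff".

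The text describes no coded tubes, no separate unblinded sample handler, no masked gating and no dummy placebo assays.

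**The concern.** If the list of tubes to be assayed depends on the arm, the list itself discloses the arm. Drawing blood at the same times in both groups keeps the schedule from revealing the arm to the subject. It does nothing for those who select, receive or read the tubes.

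The outcome at risk is the primary one. MDSC counts come from populations defined by relative expression, which may leave some room for judgement in setting gates. If the reader of the day-30 sample can tell which subjects had a day-14 assay, a modest between-arm difference could partly reflect how the gates were set, and an appeal to blinding would not answer that criticism. This is separate from which between-arm comparisons the schedule permits: the day-30 comparison can be made, but its masking is not secured.

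**Working it through.** No figure in the plan states the risk of unmasking, so the main check sets the provisions side by side. The arithmetic after it only illustrates scale.

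**1. Schedules (Laboratory Design)**

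| Time point | MMR | Placebo |
|---|---|---|
| Baseline | assayed | assayed |
| Day 14 | assayed | not assayed |
| Day 30 | assayed | assayed |
| Day 60 | assayed | not assayed |
| 12 months | not scheduled | assayed |

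A day-14 assay implies MMR with certainty. The converse is weaker, because a missing day-14 assay may be a missed visit. With equal allocation (assumed) and day-14 attendance *a*, the chance that a subject without a day-14 assay is on placebo is 0.5 / [0.5 + 0.5(1 − *a*)]. This is 100% at *a* = 1, 91% at *a* = 0.9 and 83% at *a* = 0.8; the last matches the plan's 20% loss allowance.

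**2. Order of events (Clinical Design windows).** Day 14 ± 2 is days 12-16 and day 30 ± 2 is days 28-32. The shortest gap is 28 − 16 = 12 days, so the identifying tube always comes first.

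**3. Who must know.** If only the scheduled tubes are shipped, the person selecting them uses the allocation. If all are shipped, the instruction on which to run uses it. With no whole-blood storage described, neither decision can wait until the end of the study.

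**4. The plan's detectable changes.** Inputs from the power section: means 0.22 and 0.11, SD 0.03, 25 per arm, two-sided 0.05, 80% power.
- Normal approximation: 0.03 × √(2/25) × (1.960 + 0.842) = 0.0238, so 1 + 0.0238/0.22 = 1.11 and 1 + 0.0238/0.11 = 1.22.
- The noncentral t with 48 df gives 0.0243, again 1.11 and 1.22.
- The stated 1.12 and 1.24 both correspond to a difference of 0.0264 (0.22 × 0.12 = 0.11 × 0.24), where power is 86%. A two-sided level of 0.025 would give the stated values, but the plan does not state that level. This small discrepancy does not affect the present point.

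**5. Illustration of a differential gating shift.** The shift *b*, as a fraction of the mean, is an assumption; the documents give none. With no true effect, the noncentrality is *b* × mean / [0.03 × √(2/25)] = *b* × mean / 0.00849. The chance of a two-sided significant result (48 df, 0.05) is:

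| Shift | Mean 0.22 | Mean 0.11 |
|---|---|---|
| 0% | 5% | 5% |
| 2% | 8% | 6% |
| 5% | 25% | 10% |
| 10% | 72% | 25% |

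These means describe the cell populations used for sizing (CD33+HLA-DR- and CD11b+CD15+), not the M-MDSC and G-MDSC gates of the Laboratory Design section. The table shows sensitivity, not an estimate of bias in the actual endpoint.

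**The case against.** The case on the other side has real substance.

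- The text says samples are evaluated on different schedules, not that only those tubes are sent. The laboratory can infer the arm only if it can link tubes by subject and visit and knows the arm-specific plan. Labelling is not described either way. This stands, and the conclusion about the laboratory is conditional on it.
- No role is named as blinded, and equal draw times protect the subject. This also stands. What is unprotected is the masking of sample handlers and possibly of the assessor, not the subject's blind.
- The missing figure may show fixed gates. That cannot be checked here, so the absence of a gating template cannot be asserted outright.
- Against an expected 5-10 fold change, shifts of a few per cent are trivial. That is correct if the expected effect occurs. The plan also claims adequacy down to 1.12 and 1.24, and there they are not trivial.

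A reader might go further and infer that the day-14 assay unblinds the site interviewers, so that nearly all of the 12-month symptom, fatigue and stress follow-up is compromised. The documents do not support that. CTRC staff randomize and inject, so some may know the arm from day 0 whatever the assay schedule. Fatigue and stress are also self-reported.

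**Conclusion.** The concern holds in a limited form. An explicit rule of the plan makes the day-14 and day-60 assays specific to the MMR arm, and nothing in the text offsets it. As written, whoever selects tubes must act on allocation by day 14. If tubes are linkable and the schedule is known to it, the laboratory can infer the arm at least 12 days before the day-30 sample is drawn. The plan therefore does not ensure a masked reading of its primary outcome.

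The size of any bias is unknown. It would be small beside a 5-10 fold effect and potentially important near 1.12 and 1.24. It would be wrong to conclude that blinding has been defeated, that the laboratory certainly knows the arm, or that a gating shift of any particular size has occurred. The conclusion rests on tube labelling and whole-blood storage being as undescribed in practice as they are in the text.

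**What to change.** **Main option, with no extra assays.**
- Label every MDSC tube with a random specimen number that carries no subject, visit or arm identifier.
- Give the code list and the selection of tubes to someone who already holds the allocation and who does not gate, interview or analyse. This should not be the study statistician, because that would unblind the analyst.
- Lock the gating template before any sample is decoded.
- State in the protocol that the flow laboratory is blinded.

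The cost is a code list, some handling work and a few protocol sentences. If selection is also to be hidden from the staff who pack shipments, every tube can be shipped and the laboratory told by number which to run. Assuming 30 per arm and full attendance, that adds up to 30 × 2 = 60 placebo tubes (days 14 and 60) plus 30 MMR tubes at 12 months, about 90 in all.

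**Alternative: assay both arms at the same visits.** The present schedule needs 30 × 4 + 30 × 3 = 210 assays. Adding placebo at days 14 and 60 costs about 60 more. The leak is removed entirely only if the 12-month assay is also made the same in both arms:
- dropping it from placebo gives 60 × 4 = 240 assays, a net 30 more;
- adding it for MMR gives 60 × 5 = 300, a net 90 more.

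If the 12-month assay is kept, the plan should confirm that a blood tube is taken at that optional visit, since one description of it in Clinical Design mentions only a fingerprick. The downside of this option is the assay fees.
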